10.5. Efficacy Measures

All patients who are randomized will be included in the ITT analysis population. Patients will be analyzed as randomized. The ITT analysis will be the primary efficacy analysis population (see study design and statistical considerations).

For the ITT population, missing primary or secondary endpoints due to death will be imputed as failure for the primary efficacy endpoint. Secondary endpoints will be assigned the worst possible values for all analyses.

10.6. Adverse Event Reporting

Timely, accurate, and complete reporting and analysis of safety information from clinical studies are crucial for the protection of patients, investigators and study sponsors. For the purposes of this study, adverse events will be defined and reported using the *Terms and Classifications* and *Adverse Event Reporting Rules* outlined and summarized in a diagram below:

Terms and Classifications:

Adverse Event: An adverse event (AE) is considered any untoward medical occurrence in a human subject, including any abnormal sign (for example, abnormal physical exam or laboratory finding), symptom, or disease, temporally associated with the subject's participation in research, whether or not considered related to the subject's participation in the research.

Expected Adverse Events

It is recognized that the patient population with sepsis, septic shock and related forms of critical illness who require ICU care will experience a number of common abnormalities in laboratory values, signs, and symptoms due to the severity of the underlying disease and the impact of standard therapies. Examples of these expected events include, but are not limited to:

- · Respiratory failure
- · Heart failure
- Pneumonia or other / new infection
- · DVT or PE

- · Complications related to ICU procedures
- · Death
- · Arrhythmia
- Delirium
- Bowel ischemia
- · Ileus
- · Leukopenia or leukocytosis
- · Anemia or thrombocytopenia
- · Coagulopathy (DIC)
- Hypoglycemia
- Electrolyte abnormalities

In addition, planned hospital admissions or surgical procedures for an illness or disease that existed before the patient was enrolled in the trial, or before randomization, will also not be considered study related AEs. None of these expected adverse events will be considered study related AEs, unless the events:

- (1) Are felt by the Investigator to be related to Investigational Product (See Table Below), or
- (2) Lead to discontinuation of Investigational Product.

Potentially Associated Adverse Events (PAAE): Based on the reported potential risks of vitamin C, thiamine, and/or hydrocortisone, several important risks have been identified that could be associated with administration of one or all three drugs and have been labeled as "potentially associated adverse events" (PAAE). All PAAEs occurring following randomization through the initial hospital stay will be recorded on the AE page in the EDC portal. Identified PAAEs include but are not limited to nephrolithiasis, hemolysis, (refer to **Section 13.5 Table** for a detailed list).

Serious Adverse Event: A serious adverse event (SAE) is an AE that occurs during the study (ie, after randomization through to hospital discharge or day 30 follow-up [whichever occurs first]), that fulfills one or more of the following criteria:

- 1. Results in death (for the purposes of this trial, deaths will be captured as clinical outcomes and only recorded as an SAE if deemed related to the investigational product)
- 2. Is life-threatening (places the subject at immediate risk of death from the event as it occurred)
- 3. Results in inpatient hospitalization or prolongation of an existing hospitalization
- 4. Results in a persistent or significant disability/incapacity
- 5. Results in a congenital anomaly/birth defect; OR
- 6. Is an important and significant medical event. (Based upon appropriate medical judgment, may jeopardize the subject's health and may require medical or surgical intervention to prevent one of the other outcomes listed in this definition).

Serious and Unexpected Adverse Event

Serious Adverse Events (see above) that are **Unexpected** (i.e. not consistent with the natural history of the disease under study) and deemed to be definitely or possibly study-related will be reported in an expedited manner to the DSMB (see **Reporting Rules** below).

Relationship to Investigational Product

Determination of the relationships between AEs and administration of Investigational Product is a clinical decision based on all available information at the time of the completion of the EDC. Research relatedness will be evaluated according to the following definitions:

UNRELATED	The temporal relationship between treatment exposure and the adverse event is unreasonable or incompatible and/or adverse event is clearly due to extraneous causes (e.g., underlying disease, environment)
UNLIKELY	 Must have both of the following 2 conditions, but may have reasonable or only tenuous temporal relationship to intervention: 1. Could readily have been produced by the subject's clinical state, or environmental or other interventions. 2. Does not follow known pattern of response to intervention.
REASONABLE POSSIBILITY	 Must have at least 2 of the following 3 conditions: 1. Has a reasonable temporal relationship to intervention. 2. Could not readily have been produced by the subject's clinical state or environmental or other interventions. 3. Follows a known pattern of response to intervention.
DEFINITE	 Must have all 3 of the following conditions: 1. Has a reasonable temporal relationship to intervention. 2. Could not possibly have been produced by the subject's clinical state or have been due to environmental or other interventions. 3. Follows a known pattern of response to intervention.

Adverse Event Reporting Rules

All research-related AEs, PAAEs and SAEs will be submitted electronically through the EDC.

A. Timing of reporting and duration of tracking:

AE reporting: All research-related non-serious AEs will be recorded up to the first 5 days after enrollment (up to 4 days of drug infusion and 1-day post infusion) and will be reported on the AE page of the EDC, and will be summarized at quarterly intervals for DSMB review and summarized and reported for the annual IRB continual renewal.

PAAE reporting: All non-serious PAAEs occurring following randomization through the acute hospital stay will be reported on the AE page of the EDC, and will be summarized at quarterly intervals for DSMB review and summarized and reported for the annual IRB continual renewal. PAAEs deemed to be serious will be reported as per the SAE reporting process below.

SAE reporting: All SAEs occurring following randomization through the acute hospital stay or 30-days after enrollment, whichever comes first, that are unexpected and deemed to be study related will be

reported by the Investigator or designee to the DCC by entering the event on the AE page of the EDC without delay.

These events (both PAAEs and SAE) will be followed (by the site PI) for outcome until resolution/stabilization or until 30 days from enrollment whichever comes first.

B. Reporting Procedures

i. General Reporting Guideline:

The site investigator, study coordinator, or designee is responsible for entering all AEs and SAEs and updating the information (e.g., date of resolution, action taken) in a timely manner. SAEs meeting criteria should be submitted within 72 hours.

AE, PAAE and SAE reports will include, but are not limited to: the adverse event term, subject identifier, description of the event, concomitant medication used to treat the adverse event, Investigator assessment of causal relationship to the Investigational Product and/or research participation and any other relevant information.

ii. Reporting of SAEs to the DCC:

The Investigator or designee will complete an electronic SAE Report Form, assess the causal relationship to study procedure/intervention, and enter the information in the EDC system. This initial report should describe whether the SAE has resolved or is continuing, if and how it was treated, and whether the subject continued or permanently discontinued study participation.

The DCC will review all site submitted SAEs to determine if the event is indeed an SAE. In some cases, submitted SAEs may be downgraded to a PAAE. Such PAAEs will not be forwarded to the Medical Monitor or CCC, but instead be reviewed in aggregate along with other PAAEs at quarterly intervals for DSMB review and summarized and reported for the annual IRB continual renewal.

[figure not shown]
The DCC will then contact the Medical Monitor at the CCC for review of the electronic SAE Report Form and the supporting source documents. The CCC will report to the DSMB chair for review per the DSMB charter. If an ongoing SAE significantly worsens in its intensity or the relationship to study drug changes significantly, follow-up information will be provided by the site Investigator or designee within 72 hours of knowledge of this new information using the same procedure as described for transmitting the initial report. Based on reports delivered to the DCC, the CCC will report SAEs following SIRB criteria.

iii. Reporting to the IRB:

All PAAEs and SAEs will be reported as described above to the JHU SIRB in accordance with SIRB reporting requirements and may be reported locally, as determined to be required by each relying site.

If IRB reporting is determined to be required by the relying site, the Investigator or designee will inform their local IRB of the SAE and provide them with all relevant initial and follow-up information. If only limited information is available during the initial 72-hour reporting time frame, then follow-up information will be provided promptly when it becomes available. If an ongoing SAE significantly worsens in its intensity or relationship to study drug or if new information becomes available regarding an SAE, the follow-up information will be provided within 72 hours of knowledge of this new information using the same procedure for transmitting the initial report.

The diagram below illustrates decision-making guidance and process flow for reporting of AEs by individual sites:

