The primary outcome for this trial is the number of consecutive days free of vasopressors and mechanical ventilation (VVFD) in the first 30 days after start of the Study Intervention, recorded to the nearest day. Ventilator and vasopressor free days will only accrue from the last date the patient was free of both ventilator and vasopressor support. Patients who die are scored zero VVFD, and patients who return to ventilator support or vasopressor support (as defined in the inclusion criteria) will have the VVFD count reset to zero days.

Secondary Outcomes

Secondary outcomes will be mortality at 30 days, ICU mortality, mortality at 180 days, length of ICU stay, length of hospital stay, and long-term emotional and cognitive outcomes at 180 days.

6. Study Design

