11.4.4. Safety Endpoints

Complete listings and summary tables for all safety information will be presented for subjects who are included in the Safety analysis set. Descriptive statistics (number and percentage) for adverse events and serious adverse events will be presented by treatment arm. No formal statistical analysis will be performed.

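### Non-serious PAAEs are recorded to the end of the hospital stay and summarised as crude percentages by arm, with no table over a window common to both arms

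*Combined protocol and SAP*

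**What the plan says.** Section 10.6 sets three recording windows.

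- **Ordinary AEs:** "All research-related non-serious AEs will be recorded up to the first 5 days after enrollment". The window covers up to four days of infusion plus one day.
- **PAAEs:** the definition reads "All PAAEs occurring following randomization through the initial hospital stay will be recorded on the AE page in the EDC portal". The reporting rule repeats this for the non-serious ones: "All non-serious PAAEs occurring following randomization through the acute hospital stay will be reported on the AE page of the EDC". Neither sentence sets a day limit or a relatedness condition.
- **SAEs:** "All SAEs occurring following randomization through the acute hospital stay or 30-days after enrollment, whichever comes first". The same sentence goes on to restrict reporting to events that are both unexpected and judged study related. Serious PAAEs join this route: "PAAEs deemed to be serious will be reported as per the SAE reporting process below".

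Section 13.5 lists four PAAEs: nephrolithiasis, hemolysis, hypersensitivity reactions and injection site reactions. Section 10.6 says its own list is not exhaustive.

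Section 11.4.4 states the summary: "Descriptive statistics (number and percentage) for adverse events and serious adverse events will be presented by treatment arm". It adds listings and rules out formal testing. The denominator (Section 11.3.3) is every randomized subject who received at least one administration of study drug. No time-at-risk measure is named.

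Section 4 hypothesises lower 30-day mortality, and Section 5 includes "length of ICU stay, length of hospital stay" among the secondary outcomes. Study drug stops by 96 hours (Section 8.1).

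Two other places limit collection in time. In the schedule (Section 10.2) the PAAE row ends at day 30, for patients still in hospital. Section 10.4 puts the final site visit at discharge or day 30, whichever comes first.

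**The concern.** A patient discharged on day 6 and one discharged on day 25 count equally in a percentage, although the second was at risk of a recorded PAAE for about four times as long. After dosing and the day that follows it, the non-serious PAAE window is ordinary hospital time, and its length depends on discharge and death. If treatment shortens stay, treated patients are watched for less time and can look safer with no real difference. If treatment keeps more patients alive, they are watched longer and can look less safe. The safety table would then mix drug harm with the effect on recovery, and a reader of the final report could not separate the two.

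**Working it through.** The plan states no PAAE rate, length of stay or safety precision, so there is no figure of its own to reproduce. What follows is illustration.

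**Step 1. Days observed.** Let m be mortality and L the mean stay of survivors, and assume deaths occur on average at day 7. Mean days observed are D = 7m + (1 − m)L. For uncommon events at a constant daily rate, the percentage is roughly proportional to D.

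- m = 30%, L = 14: 2.1 + 9.8 = 11.9 days.
- m = 30%, L = 12: 2.1 + 8.4 = 10.5 days (12% less).
- m = 30%, L = 10: 2.1 + 7.0 = 9.1 days (24% less).
- Mortality 40% v 20%, L = 14 in both arms: 11.2 v 12.6 days (12.5% more on treatment).
- Mortality 40% v 20%, with L = 14 v 11: 11.2 v 1.4 + 8.8 = 10.2 days (9% less on treatment).

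**Step 2. A fuller model, stopped at day 30.** Assume gamma time to discharge (shape 2, mean L), exponential death giving mortality m over 30 days, and a background event rate λ = 0.002 per day. The chance of still being observed at day t is S(t) = (1 + 2t/L)·exp(−2t/L)·(1 − m)^(t/30). The percentage with an event is the integral of λ·exp(−λt)·S(t) from 0 to 30.

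| Treated v control | Treated | Control | Apparent ratio |
|---|---|---|---|
| No drug effect, L 10 v 14, m 25% | 1.83% | 2.41% | 0.76 |
| No drug effect, L 12 v 14, m 25% | 2.13% | 2.41% | 0.88 |
| No drug effect, L 14, m 15% v 25% | 2.50% | 2.41% | 1.04 |
| No drug effect, L 14, m 10% v 30% | 2.55% | 2.37% | 1.08 |
| True rate ratio 1.4, L 10 v 14, m 25% | 2.54% | 2.41% | 1.05 |
| True rate ratio 1.2, L 12 v 14, m 25% | 2.55% | 2.41% | 1.06 |

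A simulation of 2,000,000 patients per arm agreed to within about 0.01 (0.76 and 0.87 in the first two rows).

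**Step 3. Timing of events.** Let a share q of control-arm PAAEs be tied to dosing and equally frequent in both arms. With L 10 v 14 and no drug effect, the ratio is q + (1 − q) × 0.76. That gives 0.88 at q = 0.5, 0.95 at q = 0.8 and 0.99 at q = 0.95.

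**Step 4. The day-5 window.** Integrating to day 5 instead, the no-effect ratios in the four scenarios are 0.95, 0.98, 1.01 and 1.02. True ratios of 1.4 and 1.2 show as 1.33 and 1.18.

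**Step 5. Events per patient-day over the whole stay.** If the risk is constant, this recovers the true ratio. If events cluster in the dosing period and are equally frequent in both arms, it divides equal counts by unequal time. With the days from Step 1, the result is 11.9 / 9.1 = 1.31 against treatment, with no real difference.

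**The case against.** The strongest reply is that the percentage of patients with an event in hospital is a legitimate descriptive quantity in an untested table, and that the bias is small beside the noise. At 2.4% and 250 patients per arm there are about 6 events in each arm. The 95% limits for a ratio of 1 are then a factor of exp(1.96·√(1/6 + 1/6)) ≈ 3.1 either way, so a shift of 12% to 24% could not be seen. At 1,000 per arm (about 24 events each) the factor is exp(1.96·√(1/24 + 1/24)) ≈ 1.8, still wider than the shift. This stands, and it limits the weight of the point.

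Timing also favours the plan. Injection site and hypersensitivity reactions should mostly fall within dosing, although the documents do not give their timing. Shorter stay and better survival pull in opposite directions. The table is not the only safeguard either: Section 11.4.4 plans listings, and Sections 10.6 and 13.5 plan quarterly DSMB review.

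A reader might infer more than the text supports, in four ways.

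- *All AE percentages are distorted.* Ordinary AEs are restricted to related events in the first five days, so their window is nearly the same in both arms.
- *SAEs share the problem.* SAEs, and the serious PAAEs routed with them, are filtered to unexpected, study-related events and stop at discharge or day 30. A relatedness judgement that weighs timing removes much late background.
- *PAAEs are certainly recorded whatever their cause.* The opening rule, "All research-related AEs, PAAEs and SAEs will be submitted electronically through the EDC", leaves unclear whether the qualifier reaches PAAEs. Causality is recorded in each report, so a table by relatedness is possible.
- *The three categories are pooled in one percentage.* They share a data-entry page, but Section 11.4.4 does not say that they will be pooled, and it does not name PAAEs separately.

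**Conclusion.** The point holds as a modest reporting weakness confined to non-serious PAAEs. Their observation ends with discharge or death, treatment may change both, and the only summary statistic named takes no account of time observed.

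The size cannot be derived from the documents. Under assumed mean stays of 10 to 12 days against 14, constant risk and no drug effect, the apparent ratio is about 0.76 to 0.88. A difference in mortality alone gives about 1.04 to 1.08 in the other direction. If 80% or more of events are tied to dosing, the ratio is 0.95 or closer to 1. The exposure is therefore mainly for events such as nephrolithiasis and hemolysis. This reading assumes that PAAEs entered on the AE page are counted in the adverse event table of Section 11.4.4.

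The conflict over when PAAE collection ends stands whatever the size: Section 10.6 gives no day limit, while Sections 10.2 and 10.4 stop at discharge or day 30.

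**What to change.** - **Section 11.4.4:** add a by-arm table of PAAEs from randomization to day 5, the window that Section 10.6 already uses for ordinary AEs, and keep the whole-stay percentages beside it. State that PAAEs are tabulated separately from other AEs.
- **Any whole-stay rate per patient-day:** label it supplementary, or split it at day 5, because of the constant-risk assumption shown in Step 5.
- **Section 10.6:** reconcile the end of the PAAE window with Sections 10.2 and 10.4, and say whether the relatedness qualifier in the opening reporting rule applies to PAAEs.

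The cost is one extra table and some wording. The table needs the onset date of each PAAE. Section 10.6 mentions the date of resolution but not onset, so confirm that the AE page captures it; the existing five-day rule for AEs needs the same date. The downside is that late events are absent from the day-5 table, but they remain in the whole-stay table and the listings.

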Lastly, it should be noted that falsely elevated glucose levels have been observed when measurements are made using point of care glucometers during the administration of very high dose intravenous vitamin C to burn patients (66 mg/kg/hour).^{75,76} Treatment of falsely elevated glucose could result in potentially harmful hypoglycemic events. Two studies comparing glucose levels measured by point of care devices versus central laboratory measurements show that some devices (Accu Chek by Roche Diagnostics, Indianapolis, IN, USA) overestimate actual glucose levels as serum vitamin C concentration increased up to or above $851 \,\mu M.^{77,78}$ In the phase I study by Fowler et al, patients received 50 mg/kg/day in 4 divided doses.³⁹ For a 70 kg man, this is equivalent to 3.5 g/day intravenous vitamin C. In that study, the average dav 4 vitamin C trough level was 331 µM (range: 101 - 806). Hypoglycemic events were not reported, but glucose was measured in a central laboratory. In the Marik study, 6 g/day of intravenous vitamin C was administered in 4 divided doses (as is planned for this study), and no episodes of clinically significant hypoglycemia were reported.²⁰ Further, Marik et al, measured glucose levels using the Accu-Chek Inform glucometer (Roche Diagnostics, Indianapolis, IN, USA) at the end of vitamin C infusion, and found similar glucose values as those measured in the central laboratory.⁷⁹ They concluded the fictitious hyperglycemia was not a clinically significant problem at the doses of vitamin C used in their study (and those that will be used in VICTAS).⁷⁵ However, the Marik protocol also refers to a strategy of "permissive hyperglycemia" in which insulin was not given unless glucose exceeded 220 mg/dl.⁸⁰

Given the serum vitamin C concentrations observed in the study by Fowler et al, it is reasonable to consider that some patients in the current study may develop vitamin C concentrations that could interfere with some point of care glucometers. Only one point of care glucometer has been approved by the FDA for use in the critical care setting.⁸¹ The accuracy of this device has been validated to vitamin C concentrations we will not approach, as well as many other interfering substances encountered in the critical care setting. As a safety measure, we will require that participating centers only use this point of care glucometer, or validated central or critical care laboratory devices to measure glucose in study participants.

Thiamine

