10.2. Schedule of Events

In this section, the study day terminology does not correspond to calendar days, but reflects how the data is organized in the electronic data capture (EDC) system.

SCHEDULE OF EVENTS	Enrollment & Randomization	DAY 1	DAY 2	DAY 3	DAY 4	DAY 5	ICU D/C	HOSP D/C	DAY 30	DAY 180
Procedure										
Eligibility Verification	Х									
Informed Consent	Х									
Randomization	Х									
Study Drug Admin ^a	Х	Х	Х	Х	Х					
Demographics	Х									
Anthropometrics	Х									
Source of Admission	Х									
History and Physical ^b (including comorbidity)	Х									
Respiratory support ^b	Х	Х	Х	Х	Х	Х	Х	Х	0	
Vasopressor Use (each agent and dose) ^b	Х	Х	Х	Х	Х	Х	Х	Х	0	
APACHE II°	Х									
SOFA Score ^c	Х	Х	Х	Х	Х	Х				
Vitals ^b	Х	Х	Х	Х	Х	Х				
GCS	Х	Х	Х	Х	Х	Х				
RASS ^d	Х	Х	Х	Х	Х	Х				
CAM-ICU ^d	Х	Х	Х	Х	Х	Х				
Hematology (platelets)	А	А	А	А	А	А				
Chemistry (T.bili, creatinine)	А	А	А	А	А	А				
Lactate	А	А	А							
Coagulation	А									
Pregnancy Test ^e	Х									
Central Research Labs ^f	Х	Х	Х	Х	Х					
Antimicrobial Therapy ^b	Х						Х	Х	0	
Infection Source Datab	Х						Х	Х		
Healthcare Location	Х	Х	Х	Х	Х	Х	Х	Х	0	С
Adverse Event Monitoring										
Potentially Associated	Х	Х	Х	Х	Х	Х	Х	Х	0	
Serious	Х	Х	Х	Х	Х	Х	Х	Х	0	
Subject Completion and Follow-up										
Vital Status	-						Х	Х	0	С
Renal Replacement Free Days		1						Х	0	
VVFD		1						Х	0	
Neuro-psychological Battery										С
V - Doutous of her study site										

X = Performed by study site

A = Collect if available

O = Only performed by study site if patient remains hospitalized at 30 days

C = Performed by Central Long-Term Outcomes Team

^a Note: patients that receive ≤ 3 administrations of study drug/placebo on Enrollment & Randomization day, will complete the last dose(s) on day 4 (if they remain in the ICU that long)

^b Data will be abstracted from Electronic Medical Record (EMR). Abstracted data will include baseline data, and daily data. For baseline data, use most abberant elements from the 24 hours preceding the time of randomization. For daily values, use data from as close to 8 a.m. as is possible up to day 5 or ICU discharge (whichever occurs first). Vasopressor doses will only be recorded at time of randomization. After randomization day, only report the use of vasopressors or not (yes/no).

^c Data elements collected via REDCap; score calculated centrally.

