10.3. Laboratory assessments

Though specific laboratory data or results are not required for eligibility, it is **expected** that various laboratory tests will routinely be performed by the treating clinical team. When available, recorded lab data should be from values as close to 8 a.m. daily up to day 5 or ICU discharge (whichever occurs first, see schedule of events). These tests include, but are not limited to: complete blood count including platelets with or without differential, chemistry including creatinine and total bilirubin, serum lactate, coagulation studies, blood cultures, procalcitonin (PCT), C-reactive protein (CRP), urinalysis, and arterial or venous blood gas.

Note, women of child bearing age who have not undergone a sterilization procedure cannot be considered for enrollment unless the clinical teams has demonstrated they are not pregnant via a negative pregnancy test as part of routine care.

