Due to the potential for errors in some point of care glucometers in the setting of high serum vitamin C concentrations (see section 3.5), participating sites will be required to measure glucose using a point of care device that has been validated for use in the setting of high vitamin C concentrations ⁸¹, or use devices validated for high vitamin C concentrations⁸¹ in their critical care or central laboratory. If glucose is measured in a critical care of central laboratory, approximately one milliliter of blood will be obtained from an artery or vein. The number of blood draws will depend on each patient's needs and the number of glucose measurements clinical care providers order. For sites that do not have a valid point of care glucometer, and do not want to use their critical care or central laboratory, Nova Biomedical has agreed to loan sites two Nova StatStrip devices, a charging station, and test strips. Nova Biomedical will also provide on-site training in the use of the devices. Of note, use of loaned devices in this study will require the use of venous or arterial (approximately one drop of blood per measurement) samples and NOT fingersticks. The number samples will depend on each patient's needs and the number of glucose measurements clinical care providers order. Loaned StatStrip glucometers will be validated on site as detailed in the "Procedure Manual" uploaded with this application. Sites that already use a glucometer that has been validated for use in the setting of high vitamin C concentrations should measure glucose according to their usual protocol.

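### The adverse event rules conflict, and under the specific recording rule a non-serious hypoglycaemia judged unrelated goes uncounted, although section 3.5 names that harm

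*Combined protocol and SAP*

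**What the plan says.** **The harm.** Section 3.5 warns that some point-of-care meters may read falsely high at raised vitamin C concentrations: "Treatment of falsely elevated glucose could result in potentially harmful hypoglycemic events". It then restricts glucose devices as a safety measure.

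**The expected-event filter.** Section 10.6 puts hypoglycaemia on its list of expected events and says: "None of these expected adverse events will be considered study related AEs, unless the events" are judged related to study product or lead to its discontinuation.

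**The specific recording rules in 10.6.**
- Non-serious AEs: "All research-related non-serious AEs will be recorded up to the first 5 days after enrollment", a window described as up to four days of drug plus one day.
- PAAEs: "All non-serious PAAEs occurring following randomization through the acute hospital stay will be reported on the AE page of the EDC". Section 13.5 lists four: nephrolithiasis, hemolysis, hypersensitivity reactions and injection site reactions.
- SAEs: reported to the data coordinating center when "unexpected and deemed to be study related".

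**The general wording.** Section 10.6 defines an AE irrespective of its relation to the research. Its General Reporting Guideline makes site staff responsible for entering every AE and SAE. Section 14.1 has investigators report any AE. Section 13.2 has serious events go to the single IRB whatever their cause.

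**Other data.** The chemistry row in 10.2, "Chemistry (T.bili, creatinine", names only bilirubin and creatinine, and the AE rows there are only potentially associated and serious. Section 10.3 says "recorded lab data should be from values as close to 8 a.m. daily up to day 5 or ICU discharge".

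**The analysis.** Section 11.4.4 plans counts and percentages of AEs and SAEs by arm, without a formal test.

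**The concern.** The plan identifies a route from the regimen to hypoglycaemia and builds device and laboratory checks around it, but its specific recording rule passes the event through an attribution filter. That filter suits this harm badly. The route is indirect: a false reading is treated, and low glucose follows. At the bedside, both sepsis and insulin offer a ready alternative explanation, so a case caused by the regimen could be judged unrelated.

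A by-arm count of all cases, whatever their attribution, is how a randomised trial avoids that judgement. If cases are filtered at entry, or at some sites and not others, neither the 11.4.4 table nor the quarterly DSMB summaries of recorded AEs can show reliably whether the regimen, as given with its safeguards, led to more hypoglycaemia.

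**Working it through.** No figure in the documents can be reproduced here, since they give no hypoglycaemia rate. The check traces each route by which one defined case could reach the database: non-serious, judged unrelated, study drug not stopped.

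1. **Non-serious AE rule (10.6).** The event is expected and neither exception applies, so it is not study related. The rule takes only research-related events. Not entered.
2. **PAAE rule (10.6, 13.5).** The event is not among the four listed. The definition in 10.6 is open-ended, but nothing tells a site to add hypoglycaemia. No instruction to enter.
3. **SAE rule (10.6).** Not applicable to a non-serious event.
4. **Scheduled data (10.2, 10.3).** There is no glucose row and no hypoglycaemia field. Even if glucose were recorded under the 10.3 convention, one value near 8 a.m. each day would miss events at other hours.
5. **Aggregate review (Note in 13.5).** Common sepsis events go to quarterly review. The Note's example of acute kidney injury has a scheduled variable behind it (creatinine). Hypoglycaemia has none stated, and this review is not the 11.4.4 table.
6. **General wording (10.6 definition and General Reporting Guideline; 14.1).** Read literally, this covers the event. Entered.

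Routes 1 and 6 disagree. The guideline can be read in two ways:
- It says **what** is entered: every AE, including this one. It then contradicts the research-related limit in the same section.
- It says **who** enters what the specific rules call for. There is then less contradiction within 10.6, but the event is not entered.

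Under the second reading the by-arm table omits these cases. If sites differ in their reading, capture varies by site.

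**Effect on a comparison.** Let p1 and p2 be the true proportions with hypoglycaemia in the two arms and f the share recorded, assumed equal by arm. The recorded proportions are f × p1 and f × p2, and the recorded difference is f × (p2 − p1). The absolute difference shrinks by the factor f. The documents give no value for p1, p2 or f, so no numerical size follows.

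**Serious cases.** The SAE reporting rule requires the event to be both unexpected and study related. The SAE definition in 10.6 has no such limit, the General Reporting Guideline covers every SAE, and 13.2 requires IRB reporting regardless of causality. A serious hypoglycaemia classed as expected falls outside the first and inside the others.

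**The case against.** A reader might infer that no rule captures the event and that the table is bound to miss it. The documents do not support that. The General Reporting Guideline lies inside the AE Reporting Rules and is not limited to serious or related events. Section 14.1 and the AE definition point the same way. The defect is a conflict, with a miss at sites that follow the specific rule.

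Other points on the plan's side:
- **The relatedness table in 10.6 may let some cases through.** A reasonable possibility needs two of three conditions, so timing plus a known pattern is enough even when sepsis could explain the event. The grade of unlikely requires that no known pattern be followed. Since 3.5 describes the pathway, an investigator could call such a case reasonably possible. This stands, but it leaves capture to individual judgement.
- **Aggregate review.** The examples in the 13.5 Note are illustrative, so not naming hypoglycaemia is weak evidence that it is excluded. The missing data item remains.
- **The mechanism is controlled.** Sections 3.5, 10.3 and 13.5 restrict devices and require laboratory confirmation in stated situations. These steps reduce meter error; they do not count events.
- **Prior experience.** Section 3.5 reports no clinically significant hypoglycaemia in the before-after study at the same vitamin C dose. The same section notes that study's permissive approach to high glucose, which weakens the reassurance.
- **The five-day window** covers the drug period plus a day, so attribution is the main filter, not time.
- **Unseen material.** The AE flow diagram in 10.6, the DSMB charter and the Monitoring Plan were not available and might settle the matter. Source records uploaded under 12.3 would allow later abstraction, though the available text states no such plan.

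**Conclusion.** The concern holds as a conflict in the capture rules with a specific consequence. Under the non-serious AE rule in 10.6, a hypoglycaemia that is judged unrelated and does not stop study drug is not entered. Under the general wording in 10.6 and 14.1 it is. The by-arm safety table would therefore be incomplete or uneven for a harm that 3.5 names. The wording for serious cases conflicts too.

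The size is unknown. A reader might want to put a loss of power on it, but any such figure would rest on invented event rates and recording shares, for a test that 11.4.4 does not plan. Nor do the documents show that patients are unprotected: the device and laboratory checks stand, and the gap is in counting.

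The primary and mortality analyses are not affected. The conclusion assumes that the flow diagram and charter do not already resolve the conflict. The change is worth making because a stated filter removes a named harm and the correction is small. Confidence is medium.

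**What to change.** Change data collection only; no dose or clinical rule is involved.

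1. Reconcile the AE and SAE capture wording across 10.6 (definition, expected-event list, SAE definition, Reporting Rules, General Reporting Guideline), 13.2 and 14.1, so that one statement says which events are entered.
2. Make hypoglycaemia a named event on the existing AE page, with a definition stated by the sponsor and applied identically in both arms. Record it regardless of attribution, exempt from the expected-event and research-related filters. State one collection window and say how it relates to the five-day AE window and the hospital-stay PAAE window. Amend the 13.5 Note to match.
3. Tabulate it by arm in the DSMB summaries and in 11.4.4.

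**Cost.** One AE-page item and wording changes in 10.6, 11.4.4, 13.2, 13.5 and 14.1. The real burden is that sites must review glucose results already in the chart for every patient in the window, which means 500 patients at the initial target and up to 2000 at the maximum.

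**Limits.** The count would reflect the whole regimen, because 3.5 notes that hydrocortisone also affects glucose. Detection would depend on "the number of glucose measurements clinical care providers order", which may differ by arm. Both limits should be stated beside the table.
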